**5.2 Randomization**

There will be no randomization in treatment allocation.

**5.3 Treatment Procedures**

**5.3.1 Registered into study**

Once informed consent is obtained, patients will be registered into the study. We describe below all procedures that correspond to the treatment phase of our study: "TMA and RP phase" for the first 5 patients and "TMA phase" and "RP phase" for the following 10 patients (refer to study schema).

**First 5 patients**

**"TMA and RP PHASE"**

This phase of the study will be initiated within 30 days of registration.

**5.3.2 Pre-TMA MRI (Only performed if not done within previous 6 months)**

- **mp-MRI technique** mp-MRI will be performed using a 3-T MR-750 MR-scanner (General Electric, Waukesha, WI, USA) with a pelvic 16-channel phased-array body coil. Apparent diffusion co-efficiency (ADC)-map in diffusion weighted images (DWI) with the same orientation as transverse T2 weighted (T2-w) images. Dynamic contrast enhanced (DCE) image data will be post-processed with pharmacokinetic analysis software (iCAD, Nashua, New Hampshire). Lesions suspicious for clinically significant cancer in T2w, ADC-map, iCAD-DCE will be scored on a Prostate Imaging Reporting and Data System version-2.1 (PIRADS v.2.1)

---

scale from 1-5 by dedicated radiologists with expertise in prostate MRI [43]. T2w images will be manually segmented, the prostate outlined in each MRI plane and converted into a 3D object using specialized software. The final 3D prostate model will be imported into a 3D-design software (SolidWorks Corp., Concord, MA, USA) where it will be subtracted from a pre-generated rectangular mold to create an internal cavity that mirrors the patient's prostate on MRI. The mold will be created by 3D printer (Dimension Elite 3D printer, Stratasys, Inc., Eden Prairie, MN, USA), and will be used for treatment planning.

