## 1.6 Study Overview

We propose to conduct a comprehensive single institution ‘ablate and resect’ trial on Targeted Microwave Ablation (TMA) in patients undergoing robotic RP. Briefly, we will recruit patients with localized Pca undergoing RP as their treatment of choice. Immediately or 1 mo before performing RP, we will ablate the prostate with focal TMA. TMA treatment parameters will be chosen according to the manufacturer data and will be visualized in 3D using an MRI/US image-fusion platform (KOELIS Trinity®). After the prostatectomy we will study the entire prostate so that we can determine the rate of TMA-induced cell death. We will use a histologic step-sectioning approach to process the prostate that will allow us to correlate 1:1 the histology with imaging. The results of our study will provide answers to the following important questions.

**Important question #1:** Is TMA effective in eradicating all prostatic tissue and prostate cancer cells within the ablated area?

**Important question #2:** Can TMA be safely and precisely delivered to an index lesion of the prostate using the KOELIS Trinity® platform?

**Important question #3:** Do TMA predictive treated areas dimensions correlate with ablated area as determined by histological changes measured via TTC staining post-TMA on the prostatectomy specimen?

**Important question #4:** What are the best TMA parameters to achieve maximum cell kill without causing collateral complications?

**Important question #5:** How accurately post TMA MRI predict the treated area’s dimensions correlate with ablated area as determined by histological changes.

**Important question #6:** What are the MRI findings after TMA and how the MRI correlates to histology on prostate biopsy and RP specimen?

**Important question #7:** What is the perioperative AE after TMA?

**Important question #8:** What is the feasibility and safety of RP after TMA in case of ablation failure?

A total of 15 patients will be enrolled who will be identified from patients who have elected to undergo RP as their definitive treatment for PCa.

Immediately prior to RP surgery, 5 patients will undergo TMA with one ablation in the prostate index lesion.

One month prior to RP surgery, following 10 patients will undergo TMA with one ablation in the prostate index lesion.

The number of patients included may be extended considering the need to evaluate different treatment parameters (still according to manufacturer dat).

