## **2.5 Secondary Endpoints**

- The intra/post-operative safety of the targeted microwave ablation (number and severity of device- and procedure-related adverse events,
- TMA procedure duration: probe-in / probe-out time, ablation time
- Comparison between the ablation location in the prostate as seen in the KOELIS 3D map and the ablation location observed histologically on the prostatectomy specimen
- The change in urinary functions between baseline and each follow-up visit, using IPSS score and uroflowmetry
- The change in erectile functions between baseline and each follow-up visit, using IIEF-5 score
- The change in quality of life between baseline and each follow-up visit, using EPIC-26 score
- The correlation between the treatment effect dimensions measured histologically on the prostatectomy specimen resected after TMA, compared to the predictive ablation charts provided by the manufacturer
- The correlation between the treatment effect dimensions measured histologically on the prostatectomy specimen resected one month after TMA, compared to post TMA dimensions measured on the pre-RP mpMRI.
- Evaluation of the optimal treatment parameters to maximize the cell destruction without causing collateral damage.

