### 5.3.4 Pathologic Evaluation

Following prostatectomy, the prostates will primarily be evaluated using standard-of-care diagnostic methods, and secondarily be assessed in accordance with the thermal treatment parameters. The intact prostate specimens should be received in pathology within two up to six hours of prostatectomy. Standard gross examination of prostate specimens will be done including measurement, appropriate inking for margins and serial transverse sectioning from the bladder neck across the prostate to the penile urethral margin. Digitally photographing of these sections will be done. TTC viability staining will be performed not less than 2 hours after TMA and 4 up to 6 hours after completion of prostatectomy. Macroscopic evaluation of the TTC stained sections will be performed where viable tissues would exhibit maroon color change, while ablated non-viable tissues should show absence of color change. Routine tissue processing and H&E staining will be performed. H&E stained whole mount sections of the prostatectomy specimens will be evaluated on microscopy. If indicated, IHC staining will be done.

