## **6.0 MEASUREMENT OF EFFECT**

The main effect we will measure to achieve our primary objective is the treatment effect (proportion of dead tissue - benign and cancerous) inside the TMA-treated zone on the prostatectomy specimen. The excised prostate will be sliced at 4 mm intervals. Each slice will be embedded, and a pathologist will examine slides corresponding to each slice. The pathologist will be blinded to MR and TRUS imaging results. TTC and/or H&E staining are performed to determine thermal ablation zone size/location/relationship to urethra seminal vesicles capsule and other structures.

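### No step aligns the specimen cuts with the imaging plane, despite a promised 1:1 correlation and an MRI-shaped mold, so the location endpoint mixes guidance error with slicing-plane error

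*Combined protocol and SAP*

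**What the plan says.** **The promise.** Section 1.6: "We will use a histologic step-sectioning approach to process the prostate that will allow us to correlate 1:1 the histology with imaging".

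**The mold.** In Section 5.3.2 the prostate is outlined on T2-weighted MRI, turned into a 3D model and subtracted from a block to "create an internal cavity that mirrors the patient's prostate on MRI". The section then states: "The mold will be created by 3D printer (Dimension Elite 3D printer, Stratasys, Inc., Eden Prairie, MN, USA), and will be used for treatment planning". No other use is given. The section heading limits the MRI itself: "Only performed if not done within previous 6 months". Whether a man with an earlier MRI gets a mold is not stated. Section 5.3.6 applies the same MRI technique to the 10 delayed-resection men. The ablation planning in Section 5.3.3 works from ultrasound, contours, MRI fusion and simulated zones, and does not mention the mold.

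**The specimen.** Section 5.3.4, repeated in Section 9.1, specifies standard gross examination with "serial transverse sectioning from the bladder neck across the prostate to the penile urethral margin". Section 6.0 adds: "The excised prostate will be sliced at 4 mm intervals". It also blinds the pathologist to the MR and TRUS results, and asks for the zone's size, location and relation to the urethra, seminal vesicles, capsule and other structures.

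**The endpoint.** Section 2.5 lists: "Comparison between the ablation location in the prostate as seen in the KOELIS 3D map and the ablation location observed histologically on the prostatectomy specimen". Section 10.7 says that the two locations will be recorded. It gives no distance, overlap measure or error allowance.

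**The concern.** Location on the map and location on the specimen can be compared only in a common frame. The plan describes an object that could supply much of one, a cavity in the shape of the gland on MRI, but ties it to planning. Section 9.1 is the section on correlating histology with MRI, yet it repeats the pathology text and contains no correlation step.

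This is the only listed endpoint that tests whether guidance put the ablation where it was planned, which is the second hypothesis (Section 1.5) and the precision part of question 2 (Section 1.6). If the cutting plane is tilted against the imaging plane, accurate guidance can look displaced, and a real displacement can be hidden. Sectioning cannot be repeated, and in the immediate phase each ablation template is used in one man only.

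**Working it through.** The plan gives no accuracy figure for this comparison, so there is nothing to reproduce. The geometry below is illustrative.

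**Inputs from the documents**
- Slice interval: 4 mm (6.0).
- Predicted zones, short x long axis: 1.5 x 2.5, 2.0 x 2.7 and 2.5 x 3.0 cm (4.2).

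**Assumptions, not in the documents**
- Tilt θ between the cutting plane and the MRI transverse plane: 5 to 20 degrees.
- Distance L of the zone from the pivot: 15 to 20 mm.
- Long axis of the zone along the slicing axis.

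**Step 1: shift in apparent base-to-apex level.** Shift = L × sin θ.

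| θ (degrees) | L = 15 mm | L = 20 mm |
|---|---|---|
| 5 | 1.3 mm | 1.7 mm |
| 10 | 2.6 mm | 3.5 mm |
| 15 | 3.9 mm | 5.2 mm |
| 20 | 5.1 mm | 6.8 mm |

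A shift of one full slice needs θ = arcsin(4/L): 11.5 degrees at 20 mm, 15.5 degrees at 15 mm. Against the 25 mm long axis of the smallest predicted zone, the range is 1.3/25 = 5% to 6.8/25 = 27%.

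**Step 2: sensitivity to the assumptions.** Measuring the offset along the imaging axis instead (L × tan θ) and widening L to 10 to 25 mm gives 0.9 to 9.1 mm.

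**Step 3: error from the slice interval alone.** A 4 mm interval leaves up to ±2 mm (SD = 4/√12 = 1.15 mm), with or without tilt. A mold slotted at 4 mm does not remove this.

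**Step 4: effect on dimensions.** For an ellipsoid with semi-axes a (short) and b (long), the tilted in-plane diameter is 2/√(cos²θ/a² + sin²θ/b²).

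| Zone (mm) | 5° | 10° | 15° | 20° |
|---|---|---|---|---|
| 15 x 25 | +0.2% | +1.0% | +2.2% | +4.0% |
| 20 x 27 | +0.2% | +0.7% | +1.5% | +2.7% |
| 25 x 30 | +0.1% | +0.5% | +1.0% | +1.8% |

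The extent along the slicing axis, 2√(b²cos²θ + a²sin²θ), falls by 0.1% to 3.8%. In a section through the center only one in-plane diameter is stretched, so its area grows by the same 0.1% to 4.0%. Tilt therefore affects location far more than size.

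**The case against.** - **Silence is not exclusion.** Section 5.3.2 does not restrict the mold to planning, and the pathology sections do not rule it out. This stands as a limit on wording: what can be said is that no section uses the mold, or anything else, for alignment. Unwritten use still cannot be assumed. Section 11.8 requires conduct exactly as approved, and the pathologist is blinded to the imaging.
- **There is already a frame.** A reader might infer that histologic location is recorded in an arbitrary frame. The documents do not support that. Cuts are transverse and run from the bladder neck to the urethral margin, and Section 6.0 relates the zone to named structures. This is an anatomical frame, but one with unknown tilt against the imaging.
- **The millimeters are assumed.** Correct. At 5 degrees the shift (1.3 to 1.7 mm) is below the ±2 mm from slicing alone, so material error in every man is not shown.
- **The mold supplies only part of the frame.** Also correct. It gives a pre-TMA MRI frame, whereas the KOELIS map rests on an ultrasound volume linked to MRI by elastic fusion (4.1). In the delayed men the gland may have changed over the month. These limits belong in the fix and do not remove the case for it.
- **Nothing hinges on it.** The endpoint is secondary and only recorded, and no stated decision rule uses it. That limits the weight of the point. Guidance precision is nonetheless a stated goal (1.4), and no other listed endpoint measures it.

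**Conclusion.** The point holds for the location endpoint. As written, a difference between the KOELIS map and histology combines guidance error with slicing-plane error, and the promised 1:1 match has no step behind it. The size rests wholly on the assumed tilt and pivot distance, so 1.3 to 6.8 mm is an illustration of what could occur and not an estimate for this trial.

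Two stronger conclusions are not supported. A reader might infer that the primary endpoint is compromised. Section 2.4 defines it as the TTC-assessed ablated area on the specimen, and Section 6.0 does not say that the treated zone's outline is carried over from imaging; the effect on measured area is about 0 to 4%. A reader might also infer that the delayed-phase MRI comparison fails in the same way. Sections 2.5 and 10.7 define it on dimensions, which change equally little.

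The change is cheap and should be made before the first specimen is cut.

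**What to change.** - **5.3.2:** State that the mold is also used for specimen sectioning, with slots at the 4 mm interval of Section 6.0. State that it is made from the qualifying pre-TMA MRI for every man, including those whose MRI was done within the previous 6 months.
- **5.3.4 and 9.1:** Section each specimen in its mold and record which slice corresponds to which MRI level. Report a specimen that does not fit as unregistered.
- **10.7:** For each ablation, report the 3D distance between the zone center on the KOELIS map, carried to the MRI frame through the existing MRI/US fusion, and the zone center on the mold-registered histology. State that fusion error and up to ±2 mm of slice-interval error remain in this distance.
- **Delayed men:** State that the reference is the pre-TMA MRI, so gland change over the month limits the match.

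**Cost:** protocol and pathology wording, slots in the mold design, molds for men with an earlier MRI, and imperfect fit in some delayed specimens. No added patient procedure is needed.

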### 5.3.3 TMA

**TMA preparation:** The patients are instructed to self-apply rectal 2 enemas: one the night before, one the morning of TMA; nothing per oral night prior (8hs) to TMA.

**Patient position and probe position:** The patient is brought into the operating room and general anesthesia is obtained. Prophylactic antibiotic (Levaquin 500mg IV) is administered. The patient is placed in lithotomy position. The genitalia and perineal are prepped and draped in a sterile fashion. Digital rectal exam is performed. The 3D Side Fire endocavity TRUS probe (K3DEL00, Koelis, Meylan, France) is then inserted into the rectum.

**Ablation planning:** The prostate is TRUS-scanned, the transverse and longitudinal images are acquired, the dimensions of the prostate are measured and the 3D volume of the prostate is acquired. The ultrasound (US) images are adjusted to provide optimal visualization of the prostate, rectal wall and surrounding tissues. The contours of the prostate are drawn to delineate the prostate contour, the urethra contour, the rectal wall contour. After fusion with the preoperative MRI, the ablation zones set by the manufacturer can be visualized in 3D as a simulation prior to the needle insertion.

**TMA delivery and monitoring:** Under real-time TRUS guidance, a microwave antenna is transperineally inserted into the planned-ablation area. As much as possible, the needle will be placed at the center of the index tumor to maximize the treatment effect inside the lesion. OBT-Fusion® guidance ensures the proper location of the needle with respect to the targeted index lesion. Once the needle location is confirmed and the optimal treatment parameters are chosen, the microwave generator is configured accordingly, and the treatment can start. The ablation typically lasts for a few minutes.

**Post-treatment:** After the procedure, the antenna and TRUS probe are withdrawn and the robotic RP as standard of care for the prostate cancer starts under same general anesthesia. Patients is sent to the recovery room for monitoring. After completely recovery from the anesthesia the patient stays hospital overnight or is discharged home with the urethral Foley in place. Prescriptions are provided for: bladder antispasmodic, anti-inflammatory, and antibiotics.

---

### 5.3.4 Pathologic Evaluation

Following prostatectomy, the prostates will primarily be evaluated using standard-of-care diagnostic methods, and secondarily be assessed in accordance with the thermal treatment parameters. The intact prostate specimens should be received in pathology within two up to six hours of prostatectomy. Standard gross examination of prostate specimens will be done including measurement, appropriate inking for margins and serial transverse sectioning from the bladder neck across the prostate to the penile urethral margin. Digitally photographing of these sections will be done. TTC viability staining will be performed not less than 2 hours after TMA and 4 up to 6 hours after completion of prostatectomy. Macroscopic evaluation of the TTC stained sections will be performed where viable tissues would exhibit maroon color change, while ablated non-viable tissues should show absence of color change. Routine tissue processing and H&E staining will be performed. H&E stained whole mount sections of the prostatectomy specimens will be evaluated on microscopy. If indicated, IHC staining will be done.

## Following 10 patients

### *“TMA PHASE” and 1mo delayed “RP PHASE”*

### 5.3.5 Pre-TMA MRI (Only performed if not done within previous 6 months)

#### 5.3.6 *mp-MRI technique: The same as the first 5 patients.*

#### 5.3.7 **TMA**

*TMA preparation:*

*Patient position and probe position:*

*Ablation planning:*

*TMA delivery and monitoring:* The same as the first 5 patients.

**Post-treatment:** After the procedure, the antenna and TRUS probe are withdrawn. Patients is sent to the recovery room for monitoring. After completely recovery from the anesthesia the patient stays hospital overnight or is discharged home with the urethral Foley in place. Prescriptions are provided for: bladder antispasmodic, anti-inflammatory, and antibiotics.

#### 5.3.8 **RP**

30 days ( $\pm$ 15days) after TMA, the robotic RP as standard of care for the prostate cancer starts under same general anesthesia. Just prior to RP, MRI/TRUS fusion transperineal biopsy will be performed under the same anesthesia of RP. Then the RP will be immediately carried out as per SOC. After RP, the patient is sent to the recovery room for monitoring. After completely recovery from the anesthesia the patient stays hospital overnight or is discharged home with the urethral Foley in place. Prescriptions are provided for: bladder antispasmodic, anti-inflammatory, and antibiotics.

---

## 5.4 Follow-up Procedures

First 5 patients

### *“Follow-up PHASE”*

- 5.4.1** The patient returns to clinic in 10 ( $\pm 5$ ) days after TMA and immediate RP for removal of urethral Foley and formal voiding trial. An AE assessment is performed at this time.

### *“Completion PHASE”*

- 5.4.2** Patients will do a follow-up visit 30 ( $\pm 10$ ) days after TMA and immediate RP per standard of care. Adverse effects will be assessed during this visit. Tests for perineal discomfort, PSA, IPSS, IIEF-5, EPIC-26, uroflowmetry and patient satisfaction questionnaire are assessed.

#### **5.4.3 Adverse event assessment**

Adverse events will be assessed. See section 7 for Adverse Event monitoring and reporting

---

Following 10 patients

**“Follow-up PHASE 1”**

After TMA, the patient returns to clinic in 10 ( $\pm 5$ ) days. An AE assessment is performed at this time.

**“Follow-up PHASE 2”**

**5.4.4** After TMA, the patient returns to clinic in 30 ( $\pm 10$ ) days for IPSS, IIEF-5, EPIC26, uroflowmetry, PSA, MRI and AE evaluation. These will be performed prior to RP.

**“Follow-up PHASE 3”**

**5.4.5** After RP, the patient returns to clinic in 10 ( $\pm 5$ ) days for removal of urethral Foley. An AE assessment is performed at this time.

**“Completion PHASE”**

**5.4.6** Patients will do a follow-up visit 30 ( $\pm 15$ ) days after RP per standard of care. Adverse effects will be assessed during this visit. Tests for perineal discomfort, PSA IPSS, IIEF-5, EPIC-26, uroflowmetry, and patient satisfaction questionnaire are assessed.

**5.4.7 Adverse event assessment**

Baseline adverse events will be assessed. See section 7 for Adverse Event monitoring and reporting

## 5.5

## Study Calendar

First 5 patients

	Screening visit	Treatment date			Follow-up Phase	Completion phase
		Day 0			Day 10 ( $\pm 5$ )	Day 30 day ( $\pm 10$ )
		OR pre-TMA	TMA	OR post-TMA		
Medical history	X					
Demographics	X					
Medication review	X					
Adverse Event assessment	X	X		X	X	X
Physical Exam	X				X	X
Vital Signs (temperature, pulse, respiration, BP, (height and weight -only on screening)	X				X	X
Hematology, full blood count, renal function and coags	X					
PSA measurement	X					X
Patient eligibility review, enrollment	X					
Informed Consent	X					
MRI	X					
Uroflowmetry	X					X
Catheter removal					X	
IPSS, IIEF-5 and EPIC-26 questionnaires	X					X
Urine analysis and culture	X					
Radical prostatectomy				X		
TMA delivery			X			
Pathology				X 		

1: Pathologic evaluation including TTC staining is performed immediately after RP.

Following 10 patients

	Screening visit	Treatment date			Follow-up Phase1	Follow-up Phase2	RP date	Follow-up Phase3	Completion phase
		Day 0			Day 10 (±5)	Day 30 (±5) 	Day 30 (±5)	Day 40 (±5)	60 days (±10 days)
		OR pre-TMA	T M A	OR post-TMA					
Medical history	X								
Demographics	X								
Medication review	X								
Adverse Event assessment	X	X		X	X	X	X	X	X
Physical Exam	X				X	X		X	X
Vital Signs (temperature, pulse, respiration, BP, (height and weight -only on screening)		X			X			X	X
Hematology, full blood count, renal function and coags	X								
PSA measurement	X					X			X
Patient eligibility review, enrollment	X								
Informed Consent	X								
MRI	X					X			
Uroflowmetry	X					X			X
Catheter removal					X			X	
IPSS, IIEF-5 and EPIC-26 questionnaires	X					X			X
Urine analysis and culture	X								
Intra-operative prostate biopsy							X		
Radical prostatectomy							X		
TMA delivery			X						
Pathology							X 		

---

- 2: The date of Follow-up Phase2 is scheduled 1-5 days before RP date.
- 3: Pathologic evaluation without TTC staining is performed after RP.

